3.1.4 Summary Statistics

Categorical data will generally be summarized with counts and percentages of patients. The denominator used for the percentage calculation will be clearly defined. Continuous data will generally be summarized with descriptive statistics including n (number of non-missing values), mean, standard deviation, median, Q1, Q3, minimum, and maximum.

3.1.5 Hypothesis Testing

Given the primary and key secondary endpoints along with 2 active doses, hypothesis testing will be performed in a hierarchical order to preserve the overall Type 1 error.

The 600mg dose will be tested first vs placebo. The primary and the 2 key secondary endpoints will be tested in the order as presented in section 2.3.2. Testing of these 3 endpoints will next move to the 300mg dose arm vs placebo. If during the sequential testing of these 6 hypotheses, a p-value is non-significant (at alpha = 0.05), the remaining (from that point onwards) p-values will be considered nominal and significance cannot be claimed.

No multiplicity adjustments will be applied for other secondary endpoints and exploratory parameters analysis. Since the testing of the other secondary endpoints will not involve any control of Type 1 error, all associated p-values are deemed to be nominal.

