#### 9.2 Statistical Methods

Full details of the analyses will be provided in the Statistical Analysis Plan, which will be finalized prior to database lock and unblinding.

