## 9.2.1.2 Key secondary analysis of the primary endpoint

If the primary analysis is statistically significant (p<0.05), the key secondary analysis of the primary endpoint will be conducted using the data from the 300 mg NST-4016 and placebo groups, again using the Cochran-Mantel-Haenszel test, stratified by biopsy fibrosis score

(2 levels: F1 versus F2 or F3). Due to the use of this fixed-sequence testing procedure, the key secondary analysis will be based on the use of a 2-sided test at the alpha=0.05 level of significance. However, if the primary analysis is not statistically significant, the comparison between the 300 mg NST-4016 and placebo groups will be exploratory rather than confirmatory.

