2 STUDY OVERVIEW

2.1 Study Objectives

2.1.1 Primary Objective

The primary objective is to evaluate the efficacy of different doses of NST-4016 on the resolution of nonalcoholic steatohepatitis (NASH) without worsening of fibrosis in patients with NASH without histological or clinical evidence of cirrhosis.

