2.2.2 Sample Size Determination

A sample size of 88 patients per treatment group provides 80% power to detect a treatment effect of 22% (40% responder rate for active versus 18% placebo), assuming a dropout rate of 25%.

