2.3.2 Key Secondary Efficacy Endpoints

The key secondary efficacy endpoints are:

Percentage of patients with

- fibrosis improvement, defined as greater than or equal to one stage of fibrosis improvement and no worsening of steatohepatitis (inflammation/ballooning)
- resolution of NASH (defined as disappearance of ballooning (score = 0) with lobular inflammation score 0 or 1 AND fibrosis improvement (defined as greater than or equal to one stage of fibrosis improvement)

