3.4.1 Primary Efficacy Endpoint

Primary Analysis

The primary efficacy endpoint is the percentage of patients with resolution of NASH without worsening of fibrosis. Patients without a valid Week 52 (or ET, if applicable) liver biopsy will be imputed as non-responders. The number and percentage of patients meeting the criteria for the primary endpoint will be summarized by treatment group.

The analysis of the primary endpoint will be performed using the data from the 600 mg NST-4016 and placebo groups using the Cochran-Mantel-Haenszel test, stratified by baseline biopsy fibrosis score (2 levels: F1 or F2/F3). The Cochran-Mantel-Haenszel test p-values will be reported, along with Odds Ratio and 95% confidence interval. Sample SAS code is below.

Secondary Analyses

The key secondary analysis of the primary endpoint will be conducted using data for the 300 mg NST-4016 and placebo groups, again using the Cochran-Mantel-Haenszel test, stratified by baseline biopsy fibrosis score (2 levels: F1 or F2/F3).

Sensitivity Analyses

A sensitivity analysis for the primary endpoint will be carried out using a logistic regression model with treatment group (300 mg NST-4016, 600mg NST-4016, or placebo) and baseline biopsy fibrosis score (2 levels: F1 or F2/F3) as factors. Pairwise treatment comparisons will be estimated in this model as odds ratios (NST-4016 versus placebo) along with their 95% confidence intervals and p-values. Sample SAS code is below.

Additional sensitivity analyses of the analyses described above, CMH and logistic regression, will be conducted for the primary endpoint replacing the stratification factor of baseline biopsy score with the baseline ballooning score (1 or 2).

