6 CHANGES FROM PROTOCOL-SPECIFIED STATISTICAL ANALYSES

The planned changes to the protocol-specified statistical analyses, as detailed in this SAP are:

- Key secondary efficacy endpoints added for different definitions of response fibrosis improvement and resolution of NASH with fibrosis improvement.
- cT1 demoted to exploratory endpoint (from secondary) as there is uncertainty over clinical significance.
- The primary population for all efficacy analysis updated to mITT Population, with all analyses to be repeated for the ITT Population.
- No imputation to be performed for the continuous secondary endpoints.
- ALP added to list of liver enzymes to be analyzed as secondary endpoints.

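### Should the 300 mg test of NASH resolution be freed from the two 600 mg fibrosis-related tests that SAP 3.1.5 places in front of it?

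*SAP*

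**What the plan says.** Protocol 9.2.1.1 and 9.2.1.2 set a two-step sequence on one endpoint: 600 mg against placebo on NASH resolution, then 300 mg against placebo on the same endpoint, both two-sided at 0.05. If the first step fails, "if the primary analysis is not statistically significant, the comparison between the 300 mg NST-4016 and placebo groups will be exploratory rather than confirmatory". Protocol 9.2 leaves the detail to the SAP: "Full details of the analyses will be provided in the Statistical Analysis Plan, which will be finalized prior to database lock and unblinding".

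SAP 2.3.2 adds two key secondary endpoints. The first is fibrosis improvement without worsening of steatohepatitis. The second is resolution "with lobular inflammation score 0 or 1 AND fibrosis improvement". SAP 3.1.5 tests all three endpoints at 600 mg and then says "Testing of these 3 endpoints will next move to the 300mg dose arm vs placebo". Each test is at 0.05, and everything after the first failure is nominal.

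The primary objective in SAP 2.1.1 is to "evaluate the efficacy of different doses of NST-4016 on the resolution of nonalcoholic steatohepatitis (NASH) without worsening of fibrosis". The only power statement, in SAP 2.2.2, is that 88 per group "provides 80% power to detect a treatment effect of 22% (40% responder rate for active versus 18% placebo", with 25% dropout.

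SAP section 6 records "Key secondary efficacy endpoints added for different definitions of response" but is silent on the new place of the 300 mg test. SAP 3.4.1 keeps the protocol's label: "The key secondary analysis of the primary endpoint will be conducted using data for the 300 mg NST-4016 and placebo groups".

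**The concern.** The 300 mg comparison on resolution belongs to the primary objective, and on one reading of the sample size statement it has the same 80% power as the 600 mg comparison. The SAP nevertheless makes it wait for two 600 mg endpoints that match no stated efficacy objective and have no assumed rate. The second of these can be met only by patients who already count as responders on the primary endpoint, because improved fibrosis is not worsened fibrosis. It could therefore have well under 80% power.

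One miss on either test makes every 300 mg result nominal, however small its p-value. If 300 mg resolves NASH as well as 600 mg but 600 mg narrowly fails on fibrosis, the lower dose gets no confirmatory claim. A reader who compares section 6 with the protocol would not learn that the confirmatory rule for 300 mg has changed.

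**Working it through.** **Reproducing the stated sample size.** Inputs from SAP 2.2.2: 40% versus 18%, 80% power, 25% dropout. Two-sided 0.05 comes from Protocol 9.2.1.1. With pooled variance and no continuity correction, and a mean rate of 0.29:

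n = [1.960·√(2·0.29·0.71) + 0.842·√(0.18·0.82 + 0.40·0.60)]² / 0.22² = (1.258 + 0.524)² / 0.0484 ≈ 65.6, so 66 per arm.

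66 / 0.75 = 88, as stated. Power at n = 66 is 80.2%. At two-sided 0.01 the same comparison has 58.5%.

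**The combined endpoint on its own.** Suppose the same share of resolvers improves fibrosis in both arms (assumed).
- Shares of 75%, 50% and 25% give this test power of 64%, 43% and 22%.
- If the fibrosis test always passed, the chance of a confirmed 300 mg claim would then be at most 55%, 37% and 19%, against 69% in the protocol order (300 mg at 40%).
- This is not a general ceiling. If 75% of 600 mg resolvers but 50% of placebo resolvers improve (also assumed), the test has 88% power and the SAP order gives 300 mg about 66%, close to the 69%.

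**Both tests, and an alternative rule.** The alternative tests 600 mg resolution first at 0.05. If it succeeds, the two 600 mg key secondary endpoints are tested in order at 0.04 and 300 mg resolution at 0.01, and each branch passes its alpha to the other on success. After the first test 0.04 + 0.01 = 0.05, so familywise error is controlled. Simulated false benefit claims are 2.2–2.5%, against a limit of 2.5%.

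Simulation inputs:
- 66 per arm, in strata of 13 and 53 (from the 20% cap on F1), with a shared placebo arm and the Cochran-Mantel-Haenszel test.
- Resolution 18% on placebo and 40% on 600 mg.
- Assumed: placebo fibrosis improvement 12%, 19.5% or 27%; 600 mg advantage 0, 6.5, 12.5, 19.5 or 26.5 points; correlation 0.35 between resolution and fibrosis improvement.
- 200,000 trials per scenario. Simulated power for 600 mg resolution is 80–81%, which agrees with the plan.

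Ranges below run over the 15 fibrosis scenarios:

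| 300 mg resolution | Confirmed 300 mg claim, SAP order | Same, alternative | Gain (points) | Cost, 600 mg fibrosis claim | Cost, 600 mg combined claim |
|---|---|---|---|---|---|
| 40% | 2–61% | 53–67% | 5–52 | 0.1–1.1 | 0.1–1.3 |
| 30% | 1–31% | 16–32% | 1–15 | 0.3–2.7 | 0.3–3.0 |
| 25% | 1–14% | 5–14% | 0.1–4.8 | 0.4–3.2 | 0.4–3.4 |
| 18% | 0–2% | 0–2% | under 1 | 0.4–3.4 | 0.4–3.7 |

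**Where the trade turns.**
- At 30% with a 19.5-point fibrosis advantage, the gain is 2.6–3.7 points. The cost is 1.7–2.5 on the fibrosis claim and 2.8–3.0 on the combined claim.
- At 25% with a 12.5-point advantage, the gain is 1.8–2.4 and the costs are 2.6–3.4.
- At 25% with 19.5 points or more, the gain is under 1 and the costs are 0.6–3.4.

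**What the SAP order buys.** If the protocol order were kept and the 600 mg fibrosis test placed after 300 mg resolution, the chance of a confirmed 600 mg fibrosis claim would fall by up to 11 points (300 mg at 40%) or 45 points (300 mg at 30%). Moving the 300 mg test back is therefore not free.

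**The case for a change.** The strongest case for a change is that the possible loss is large and the remedy small. With 300 mg at 40%, the SAP order can leave as little as a 2% chance of a confirmed 300 mg claim, while the alternative never falls below 53%. It leaves the 600 mg primary test untouched and costs no other 600 mg claim more than about 4 points. The edit is a few sentences made before unblinding. All of that arithmetic stands.

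It does not establish an error. The largest gain needs 300 mg to match 600 mg on resolution while 600 mg has no fibrosis effect at all. Protocol 5.2 expects a dose-response relationship. Protocol 1.4.1.2 reports significant falls in Pro-C3 and ELF at both doses. Serum markers do not fix histology rates, but they make that corner a weak basis for redesign. In the zero-effect rows the model also makes placebo resolvers improve fibrosis more often than 600 mg resolvers (36% versus 26% at the lowest placebo rate), an artefact of holding the correlation fixed. At 25% to 30% resolution on 300 mg, gain and cost are often of similar size. The 0.01 share is itself one choice among many.

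The point about objectives proves too much. The SAP's secondary objectives cover only safety and pharmacokinetics, so no secondary efficacy endpoint would pass that test. The two endpoints are named in 2.3.2 and declared in section 6.

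The documentation point is correct. Section 6 omits the move from second to fourth, and the 3.4.1 label belongs to the protocol's scheme. But 3.4.1 sets no alpha and no gate, and 3.1.5 sets both without ambiguity, so an analyst reaches the same result either way.

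**Conclusion.** No change to the plan is needed. SAP 3.1.5 is an ordinary fixed sequence: complete, unambiguous, set before treatment codes are released, and valid for familywise error. It ranks all the 600 mg claims above any 300 mg claim. That is a sponsor's priority, and statisticians could reasonably rank the claims differently.

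The alternative would add about 5 to 52 points to the chance of a confirmed 300 mg claim if 300 mg resolution is 40%, 1 to 15 at 30%, 0 to 5 at 25% and under 1 at 18%. It would cost up to about 4 points on each 600 mg key secondary claim. These figures assume 66 evaluable per arm, the resolution rates in SAP 2.2.2 for placebo and 600 mg, and fibrosis rates and a correlation that neither document gives. Which side of the trade looks better depends on those unstated rates and on how much a 300 mg claim is worth against a 600 mg fibrosis claim.

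The missing line in section 6 and the leftover label in 3.4.1 are clerical. The 300 mg comparison is analysed and reported in any case; only its status as confirmatory or nominal depends on the order, and 3.1.5 settles that.

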3.1.6 Handling of Dropouts and Missing Data

Date Values

In cases of incomplete dates (e.g., AE, concomitant medication, and medical history start and/or stop dates), the missing component(s) will be assumed as the most conservative value possible. For example, if the start date is incomplete, the first day of the month will be imputed for the missing day and January will be imputed for the missing month. If a stop date is incomplete, the last day of the month will be imputed for the missing day and December will be imputed for the missing month. Incomplete start and stop dates will be listed as collected without imputation.

Date imputation will only be used for computational purposes such as treatment-emergent status. Actual date values, as they appear in the original case report forms (CRFs), will be presented within the data listings.

Non-Date Values

Missing values for the primary endpoint, Week 52 (or at the early termination (ET) visit, if applicable) liver biopsy will be imputed as nonresponders.

All other efficacy and safety data will be used according to availability, with no imputation for missing data.

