## 9.2.2 Analysis of Safety

Safety variables will be tabulated and presented for the Safety Population.

Baseline will be defined as the predose value at Visit 2 (Week 0); if this value is missing, then the latest predose value will be used.

A TEAE is defined as a new or worsening adverse event after the first dose of study drug. The number and percentage of patients with at least 1 TEAE will be summarized by treatment group by system organ class and preferred term. Similar summaries will be presented for study drug-related TEAEs and SAEs.

Safety laboratory parameters, vital signs, and ECGs will be summarized by treatment group by visit. Change from baseline values by visit will also be presented for the continuous parameters. The number (and percentage) of patients with abnormalities based on predefined normal ranges will be tabulated by treatment group.

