3.6.1 Adverse Events (AEs)

An adverse event is defined as any untoward medical occurrence in a clinical investigation patient administered a pharmaceutical product, which does not necessarily have a causal relationship with this treatment. An adverse event can therefore be any unfavorable and/or unintended sign (including an abnormal laboratory finding), symptom, or disease temporally associated with the use of an investigational medicinal product, whether or not related to the investigational medicinal product. A treatment emergent AE (TEAE) is defined as a new or worsening adverse event after the first dose of study drug.

All AEs will be coded to system organ class and preferred term using MedDRA version 22.0.

An overview of AEs will be provided including counts and percentages of patients and number of events by treatment group and overall for Safety Population (and event counts) with the following:

- Any Adverse Event
- Any TEAEs
- Maximum severity of TEAEs
- Study drug related TEAEs
- Maximum severity of study drug related TEAEs
- TEAEs leading to discontinuation of study drug
- Any TEAEs of special interest (TEAESI)
- Any serious TEAEs (TESAEs)
- Study drug related TESAEs
- TESAE/TEAESIs leading to discontinuation of study

- TESAEs leading to death
- TESAEs related to COVID leading to death

The TEAEs described above will be summarized separately by System Organ Class and Preferred Term (and by maximum severity).

Listings will be presented specifically for all TEAEs, TEAESI, TESAEs, TEAEs Leading to Discontinuation of Study Drug, TEAEs Leading to Discontinuation of Study and TESAEs Leading to Death.

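### The SAP's rule for incomplete adverse-event start dates can class on-drug events as pre-treatment, contrary to its own stated principle

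*SAP*

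**What the plan says.** SAP Section 3.1.6 has one rule for all partial dates. Its scope is "In cases of incomplete dates (e.g., AE, concomitant medication, and medical history start and/or stop dates", so adverse-event onset is covered by name. The principle given is that "the missing component(s) will be assumed as the most conservative value possible". The example that follows gives the rule for start dates: "the first day of the month will be imputed for the missing day and January will be imputed for the missing month". The section then says what the imputed dates are for: "Date imputation will only be used for computational purposes such as treatment-emergent status".

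SAP Section 3.6.1 supplies the definition on which the date acts: "A treatment emergent AE (TEAE) is defined as a new or worsening adverse event after the first dose of study drug". Protocol Section 9.2.2 has the same definition and no rule for partial dates.

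In SAP Section 3.6.1 the overview table has one row open to all events, "Any Adverse Event". Its other rows concern treatment-emergent events: severity, relatedness, special interest, seriousness, discontinuation and death. The detailed tables follow suit: "The TEAEs described above will be summarized separately by System Organ Class and Preferred Term (and by maximum severity". The adverse-event listings named there are also limited to treatment-emergent events. SAP Section 7 separately promises listings of all available data.

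**The concern.** For an adverse-event onset, the earliest possible date is the least cautious choice, because it moves the event towards the period before treatment. Events are collected from consent (Protocol Section 8.1), so a pre-treatment class exists for them to fall into.

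With only the day missing, the rule fails most often for onsets soon after first dose, which is where tolerability problems tend to be looked for. The first scheduled assessment after the dosing visit is Week 4, plus or minus 5 days (Protocol Section 6.3.2 and Appendix A), so an onset in the first weeks may be recalled some time later. Safety and tolerability are the protocol's secondary objective, and its interim summary names one tolerability exception: mild nausea at 4.3%, 9.0% and 21.3% on placebo, 300 mg and 600 mg (Section 1.4.1.3). Losing a share of such events would understate both the rates and the absolute differences between arms.

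**Working it through.** The plan gives no figure to reproduce. The check applies the rule to the calendar.

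**Assumptions (not from the documents).** First dose is equally likely on each of the 365 days of a non-leap year. True onset is equally likely on each day of a window after first dose, counted from day 1 or from day 0. An event is misclassified if its imputed start date falls before the first-dose date; an imputed date equal to the first-dose date counts as treatment-emergent.

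**Example, first dose 15 March 2021.**
- Onset 20 March, recorded as March 2021: imputed 1 March, pre-treatment.
- Onset 2 April, recorded as April 2021: imputed 1 April, still a TEAE.
- Onset 20 November, recorded as 2021: imputed 1 January, pre-treatment.

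**Day missing.** For an onset k days after first dose, the error needs the same calendar month and a first dose after the 1st. A month of L days has max(L − 1 − k, 0) such first-dose dates. Summed over 12 months, for k up to 27, this is 365 − 12 − 12k = 353 − 12k. Averaging over the window:
- Days 1–7, mean k = 4: (353 − 48)/365 = 305/365 = 83.6%. Days 0–7, mean k = 3.5: 311/365 = 85.2%.
- Days 1–14, mean k = 7.5: 263/365 = 72.1%. Days 0–14, mean k = 7: 269/365 = 73.7%.
- Days 1–28, mean k = 14.5: 179/365, plus 1/(28 × 365) because February contributes 0 rather than −1 at k = 28, gives 49.1%. Days 0–28, by the same steps: 185/365 + 1/(29 × 365) = 50.7%.
- Days 1–364: each month contributes (L − 1)(L − 2)/2, so 7 × 435 + 4 × 406 + 351 = 5,020. Divided by 365 × 364 = 132,860, this is 3.8%.
- Days 0–378: each month contributes L(L − 1)/2, so 7 × 465 + 4 × 435 + 378 = 5,373. Divided by 365 × 379 = 138,335, this is 3.9%.

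**Day and month missing.** The error needs the same calendar year and a first dose after 1 January, which leaves 364 − k first-dose dates out of 365.
- Days 1–7: 360/365 = 98.6%. Days 1–28: 349.5/365 = 95.8%.
- Days 1–364: (363 × 364/2)/132,860 = 66,066/132,860 = 49.7%.
- Days 0–378: (364 × 365/2)/138,335 = 66,430/138,335 = 48.0%.

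**With a first-dose floor.** An on-drug event always has known date parts compatible with onset on or after first dose, so its imputed date cannot precede first dose. The misclassified share is 0% in every case above.

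**Illustration of the overall effect.** The share of events with partial dates is not in the documents, so take 1% to 10% of nausea events lacking the day, one event per patient, and 51% to 85% of those misclassified. The fraction lost is q = 0.01 × 0.51 = 0.0051 up to 0.10 × 0.85 = 0.085. With 21.3% of the planned 88 patients, or 18.7, that is 0.1 to 1.6 patients. At the upper end 21.3% becomes 21.3 × 0.915 = 19.5%. If q is equal in all arms, the 600 mg minus placebo difference of 17.0 points becomes 17.0 × 0.915 = 15.6 points, and the risk ratio does not change.

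**The case against.** The strongest defence has four parts.

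First, the governing sentence asks for the most cautious value, the first-of-month rule is only its example, and SAP Section 7 defers detail to programming specifications that could add a floor. This does not rescue the text. For adverse-event onset the example contradicts the principle, neither document states a floor, and a programmer is likely to code the explicit instruction.

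Second, partial dates should be uncommon. Protocol Section 10.1.5 sends missing data back to sites as queries, Section 10.1.1 treats an eCRF as complete only once missing data are accounted for, and serious and special-interest events are reported within 24 hours. Visits at Weeks 0, 4, 10 and 16 bracket early onsets, and a year-only onset is hard to imagine for an event elicited at such visits. This stands. It limits the size of the problem but does not correct the rule.

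Third, affected events are not lost from the report: they remain in the "Any Adverse Event" row and the general listings. An event recorded as worsening after first dose might still qualify as treatment-emergent, although the SAP does not say how that works with a partial date. This also stands.

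Fourth, safety is summarised descriptively. The SAP's hierarchical tests concern efficacy only, so no test depends on this derivation.

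A reader might go further and infer that early on-drug events in general will vanish from the safety tables, that about half of all on-study events are lost, or that a nausea signal will be hidden. The documents support none of these. The percentages apply only to events with incomplete start dates, the figure near one half only to those lacking both day and month, and the protocol gives no onset times for nausea.

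**Conclusion.** The rule as written is wrong for adverse-event start dates. It errs in one direction, towards fewer treatment-emergent events, and conflicts with the principle stated beside it.

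Among on-drug events with only the day missing, it misclassifies about 84–85% with onset within 7 days, 72–74% within 14 days, 49–51% within 28 days and 4% over the study. With day and month missing, it misclassifies about 48–50% over the study. The ranges reflect whether onset is counted from day 1 or day 0 and, for the whole study, a window of 364 or 378 days. They rest on uniform first-dose and onset dates.

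The overall effect depends on how many events have partial dates, which the documents do not give, and is probably small. The rule should be corrected, but it does not threaten the trial's main conclusions.

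**What to change.** In SAP Section 3.1.6, give adverse-event start dates their own rule:

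- If the known parts of the date do not place onset before first dose, and the stop date does not show resolution before first dose, impute the later of the first-dose date and the earliest date that the known parts allow, and count the event as treatment-emergent.
- Count an event with a wholly missing start date as treatment-emergent unless its stop date precedes first dose.
- Keep the present rule for medications and medical history.

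The cost is about two sentences in the SAP and one derivation in the ADaM specification. A few events that truly began before dosing will be counted as treatment-emergent. That is the cautious direction for safety, and there is no reason to expect it to differ by arm.

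The change belongs before database lock. SAP Section 5.2 places unblinding after lock, and SAP Section 1 requires later deviations to be documented in the study report, where a change to treatment-emergent status could look data-driven.
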